9.4 Database management and quality control

For studies using eCRFs, Novartis personnel (or designated CRO) will review the data entered by investigational staff for completeness and accuracy. Electronic data queries stating the nature of the problem and requesting clarification will be created for discrepancies and missing values and sent to the investigational site via the EDC system. Designated investigator site staff are required to respond promptly to queries and to make any necessary changes to the data.

Concomitant treatments and prior medications entered into the database will be coded using the WHO Drug Reference List, which employs the Anatomical Therapeutic Chemical classification system. Medical history/current medical conditions and adverse events will be coded using the Medical dictionary for regulatory activities (MedDRA) terminology.

Samples and/or data (e.g., safety laboratory assessment [REDACTED] samples) will be processed centrally and the results will be sent electronically to Novartis (or a designated CRO).

PRO data collected using an electronic tablet device will be documented into a separate study specific database supplied and managed by a designated vendor. All PRO data will be sent electronically to Novartis personnel (or a designated CRO).

Data about patient enrollment, discontinuation of study treatment, and medication numbers (if applicable) for study treatment dispensed via IRT (in countries that are supplied by Novartis DSM) will be tracked using an Interactive Response Technology. The system will be supplied by a vendor(s), who will also manage the database. The data will be sent electronically to Novartis personnel (or designated CRO).

The occurrence of any protocol violations will be determined. After these actions have been completed and the data have been verified to be complete and accurate, the database will be declared locked and made available for data analysis. Authorization is required prior to making any database changes to locked data, by joint written agreement between the Global Head of Biostatistics and Data Management and the Global Head of Clinical Development.

For EDC studies, after database lock, the investigator will receive a CD-ROM or paper copies of the patient data for archiving at the investigational site.

10 Statistical methods and data analysis

The primary efficacy and safety analyses will be conducted after all patients have completed 6 cycles of study treatment or have discontinued early. The primary analysis will be summarized in the primary CSR based on the Full Analysis Set (FAS). The final analysis will be performed at the end of the study and will be summarized in the final study CSR. Data analysis cut-off dates will be determined and the primary and the final analyses, and all data captured in the study up to the respective cut-off date will be analyzed and reported.

- The primary efficacy and selected safety analyses will also be performed for the following subgroups:
- Line of therapy (2nd / 3rd).

- 2nd line therapy: all patients who received only one line of prior antineoplastic therapy before the start of study treatment
- 3rd line therapy: all patients who received two lines of prior antineoplastic therapy before the start of study treatment (treatment with immune checkpoint inhibitor must have been the last treatment prior to study entry)
- Age category
- MSKCC and IMDC risk groups

Further details will be included in the Statistical Analysis Plan (SAP).

10.1 Analysis sets

10.1.1 Full Analysis Set

The FAS comprises all patients to whom study treatment has been assigned and who received at least one dose of pazopanib.

10.1.2 Safety Set

The Safety Set includes all patients who received at least one dose of pazopanib. The safety set and the FAS are the same for this single arm phase II study.

10.1.3 Per-Protocol Set

The Per-Protocol Set (PPS) consists of a subset of the patients in the FAS who are compliant with requirements of the protocol.

The protocol deviations **potentially** leading to exclusion from the PPS are:

- Diagnosis at screening different from histologically confirmed locally recurrent or metastatic predominantly clear cell renal cell carcinoma.
- No previous systemic therapy with an immune checkpoint inhibitor either as monotherapy or in combination therapy, or more than two previous line of anti-cancer systemic therapy.
- No measurable lesions at baseline.
- Another anti-neoplastic therapy administered after start of study treatment and prior to the first tumor assessment.

10.1.4 Other analysis sets

Not applicable.

10.2 Patient demographics/other baseline characteristics

Demographic and other baseline data including disease characteristics will be listed and summarized descriptively for all patients in the FAS.

Categorical data will be presented as frequencies and percentages. For continuous data, mean, standard deviation, median, minimum, and maximum will be presented.

Relevant medical histories and current medical at baseline will be summarized by system organ class and preferred term.

10.3 Treatments (study treatment, concomitant therapies, compliance)

The Safety set will in general be used for the analyses of treatments. Categorical data will be summarized as frequencies and percentages. For continuous data, mean, standard deviation, median, 25th and 75th percentiles, minimum, and maximum will be presented.

The duration of exposure to pazopanib (expressed in months), the dose intensity (computed as the ratio of actual cumulative dose received and actual duration of exposure) and the relative dose intensity (computed as the ratio of dose intensity and planned dose intensity) will be summarized by means of descriptive statistics.

The number of patients with dose adjustments (reductions, interruption, or permanent discontinuation) and the corresponding reasons will be summarized for the study treatment. All pazopanib dosing data will be listed.

Concomitant medications and significant non-drug therapies prior to and after the start of the study treatment will be listed and summarized according to the Anatomical Therapeutic Chemical (ATC) classification system in the Safety set.

Anticancer therapies administered after the discontinuation of the study treatment will be listed and summarized according to the ATC classification system.

10.4 Primary objective

The primary objective of the study is to evaluate the efficacy of pazopanib as assessed by PFS based on local investigator assessment per RECIST v1.1 in patients with locally advanced/metastatic RCC with predominantly clear cell component after previous therapy with immune checkpoint inhibitor treatment.

10.4.1 Variable

The primary efficacy variable of the study is PFS, defined as the time from the date of start of pazopanib treatment to the date of the first documented progression or death due to any cause. PFS will be assessed via local review according to RECIST 1.1 (see [Appendix 2](#) for further details).

10.4.2 Statistical hypothesis, model, and method of analysis

No formal hypothesis will be tested in the study. An estimation of the median PFS with 95% confidence intervals will be provided in the FAS population. The Kaplan-Meier estimate of the PFS survival function will be estimated and displayed. The resulting median PFS time will be given with 95% confidence intervals, as well as 25th and 75th percentiles will be reported.

PFS probability at selected time-points (e.g., 3, 6 and 12 months) will also be estimated.

10.4.3 Handling of missing values/censoring/discontinuations

In the primary analysis, PFS will be censored at the date of the last adequate tumor assessment if no PFS event (disease progression or death due to any cause) is observed prior to the analysis cut-off date.

Only tumor assessments with a reported tumor response status of CR, PR or SD will be considered adequate to determine the censoring date.

If a PFS event is observed after two or more missing or non-adequate tumor assessments, then PFS will be censored at the last adequate tumor assessment before the PFS event. If a PFS event is observed after a single missing or non-adequate tumor assessment, the actual date of the event will be used.

10.4.4 Supportive and sensitivity analyses

As a supportive analysis, PFS may be analyzed based on the Per Protocol Set, using the same analysis conventions as in the primary efficacy analysis.

In addition, subgroup analysis by line of therapy subgroup (2nd/ 3rd), age category and MSKCC and IMDC risk groups will be performed in the FAS for PFS as appropriate. Details will be provided in the SAP.

10.5 Secondary objectives

The secondary efficacy and safety objectives that will be evaluated in the study include:

- ORR and CBR based on local investigator assessment as per RECIST 1.1
- OS
- DOR in the subset of patients with confirmed CR / PR;
- safety and tolerability
- PRO assessed by EQ-5D and FKSI-DRS questionnaires.

10.5.1 Key secondary objective(s)

Not applicable

10.5.2 Other secondary efficacy objectives

Overall response rate (ORR)

ORR is defined as the proportion of patients with best overall response (BOR) of CR or PR based on local investigator's assessment according to RECIST 1.1 (see [Appendix 2](#) for details). Determination of BOR of PR or CR will be based on confirmed PR/CR as per RECIST 1.1.

ORR will be calculated based on the FAS and its exact 95% confidence interval ([Clopper and Pearson 1934](#)) will be presented.

Clinical benefit rate (CBR)

CBR is defined as the proportion of patients with a best overall response of confirmed CR, or PR or an overall lesion response of SD or Non-CR/Non-PD lasting ≥ 24 weeks based on local investigator's assessment according to RECIST 1.1.

CBR and its exact 95% confidence interval will be provided using FAS population.

Overall survival (OS)

OS is defined as the time from date of start of pazopanib treatment to date of death due to any cause. If a patient is not known to have died, then OS will be censored at the latest date the patient was known to be alive (on or before the cut-off date).

OS will be analyzed in the FAS population. The OS distribution will be estimated using the Kaplan-Meier method. The Kaplan-Meier curve will be graphically presented, and the median, 25th and 75th percentiles will be shown along with the corresponding 95% confidence intervals. OS probability at selected time-points (e.g., 6, 12 and 24 months) will also be estimated.

Duration of response (DOR)

DOR only applies to patients, whose best overall response is confirmed CR or PR, as per local investigator's assessment, according to RECIST 1.1. DOR is defined as the time from the date of first documented response of CR or PR (i.e., the start date of response, not the date when response was confirmed), to the date of the first documented progression or death due to underlying cancer, whichever comes first. In patients continuing without progression or death due to underlying cancer DOR will be censored at the date of their last adequate tumor assessment. DOR will be estimated using the Kaplan-Meier method. The median, 25th and 75th percentiles, and the corresponding 95% confidence intervals will be provided.

10.5.3 Safety objectives

10.5.3.1 Analysis set and grouping for the analyses

For all safety analyses, the safety set will be used. Summary table and patient data listings will be used to analyze and present safety data.

The overall observation period will be divided into three mutually exclusive segments:

1. pre-treatment period: from day of patient's informed consent to the day before first dose of study medication;
2. on-treatment including safety follow-up period: from day of first dose of study medication to 30 days after last dose of study medication;
3. post-treatment period: starting at day 31 after last dose of study medication.

If dates are incomplete in a way that clear assignment to pre-, on-, post-treatment period cannot be made, then the respective data will be assigned to the on-treatment period.

For the safety evaluations (with the exception of AEs), the last available assessment performed on or before the date of study treatment start will be considered as the "baseline" assessment.

10.5.3.2 Adverse events (AEs)

Summary tables for adverse events (AEs) will include only AEs that started or worsened during the on-treatment period, the **treatment-emergent** AEs.

The incidence of treatment-emergent adverse events (new or worsening from baseline) will be summarized by system organ class and or preferred term, severity (based on NCI-CTCAE grades), relation to study treatment.

Serious adverse events, non-serious adverse events, adverse events of special interest (AESI) (see [Section 8.1.3](#)) and adverse events leading to study treatment discontinuation during the on-treatment period will be tabulated for safety set as well as by line of therapy subgroup (2nd/3rd), age category and MSKCC and IMDC risk groups.

All deaths (on-treatment and post-treatment) will be summarized.

All AEs, deaths and serious adverse events (including those from the pre and post-treatment periods) will be listed and those collected during the pre-treatment and post-treatment period will be flagged.

10.5.3.3 Laboratory abnormalities

Grading of laboratory values will be assigned programmatically as per NCI Common Terminology Criteria for Adverse Events (NCI-CTCAE) version 4.03. The calculation of NCI-CTCAE grades will be based on the observed laboratory values only, clinical assessments will not be taken into account.

NCI-CTCAE Grade 0 will be assigned for all non-missing values not graded as 1 or higher.

For laboratory tests where grades are not defined by NCI-CTCAE v4.03, results will be categorized as low/normal/high based on laboratory normal ranges.

For laboratory tests where grades are defined by NCI-CTCAE v4.03:

- Worst post-baseline NCI-CTCAE grade (regardless of the baseline status). Each patient will be counted only once for the worst grade observed post-baseline.
- Shift tables using NCI-CTCAE grades to compare baseline to the worst on-treatment value

For laboratory tests where grades are not defined by NCI-CTCAE v4.03:

- Shift tables using the low/normal/high/ (low and high) classification to compare baseline to the worst on-treatment value.
- Laboratory abnormalities will be summarized for safety set as well as by line of therapy subgroup (2nd/3rd), age and MSKCC and IDMC risk groups, as appropriate.

Listing of all laboratory data with values flagged to show the corresponding NCI-CTCAE v4.03 grade if applicable and the classifications relative to the laboratory normal ranges will be generated.

10.5.3.4 Other safety data

ECG

- Local 12-lead ECGs including HR, PR, QRS, QT, and QTcF intervals will be obtained for each subject at baseline, during the study treatment period and at the end of treatment. ECG data will be read and interpreted locally.
- The number and percentage of patients with notable ECG interval values and change from baseline ECG parameters by time point will be summarized in the Safety set.
- All collected data will be presented in data listings; notable values and abnormality finding will be flagged in the listing.

Echocardiogram/MUGA

- Local echocardiogram or MUGA will be obtained for each subject at baseline, during the study treatment period and at the end of treatment.
- Ejection fraction values will be classified based on NCI-CTCAE v4.03 and a shift table will be prepared for the Safety set to summarize the distribution of individual worst on-treatment values vs. the corresponding baseline values.
- All collected data will be presented in data listings and notable values will be flagged.

Vital signs

- Data on vital signs will be tabulated and listed, notable values will be flagged.

10.5.3.5 Supportive analyses for secondary objectives

Not applicable.

10.5.3.6 Tolerability

Tolerability will be assessed by evaluating the incidence of drug-related adverse events by NCI-CTCAE grade and the incidence of events leading to study treatment discontinuation (see [Section 10.5.3.2](#)).

10.5.4 Resource utilization

Not applicable.

10.5.5 Patient-reported outcomes

[figure not shown]
The FAS will be used for analyzing the PRO data unless specified differently. The EQ-5D-5L and FSKI-DRS will be used to collect PRO data on the subject's health-related quality of life and disease-related symptoms.

The EQ-5D-5L is a general health status and health utility measure ([Rabin 2001](#)) and measures 5 dimension of health state: mobility, self-care, usual activities, pain/discomfort, and anxiety/depression each assessed by a single question on a five-point ordinal scale EQ-5D Visual Analog Scale (VAS) is also included. The FSKI-Disease Related Symptoms (FSKI-DRS) is a 9-item questionnaire specifically designed to evaluate symptoms that are directly attributable to kidney cancer ([Cella 2007](#)) and includes patient's symptoms in the past seven days such as lack of energy, pain, bone-pain, shortness of breath, fatigue, blood in urine, etc. The scoring of these instruments will be done in accordance with the respective user's manual of the instrument.

Handling of missing data and generation of standard scores for the analysis will be performed in accordance with the respective scoring manual.

Descriptive statistics (mean, standard deviation, median, minimum, and maximum) will be used to summarize the scored scales at each scheduled assessment time point. Additionally, changes from baseline in the scores at the time of each assessment will be descriptively analyzed. Additional statistical analyses such as repeated measures analysis for changes of the mean scores over time will be performed as appropriate. Patients with an evaluable baseline score and

at least one evaluable post baseline score during the treatment period will be included in the analysis of the changes from baseline. Summary tables and plots will be reported. All reported data will be presented in data listing.

10.7 Interim analysis

No formal interim analysis is planned for this trial.

10.8 Sample size calculation

Since there is no formal hypothesis testing, sample size for this study is not based on any statistical power consideration. A total of approximately 100 patients (with approximately 40 patients receiving pazopanib as 2nd-line therapy) are planned to be enrolled and treated in this study. In a retrospective study, Nadal et al. reported median PFS (mPFS) of 6.9 months (95% CI: 3.7 to 10.1) in mRCC patients treated with VEGFR-TKI therapy after any PD-1 combination (Nadal et al 2016). Based on this data, the median PFS for this patient population treated with pazopanib following prior treatment with immune checkpoint inhibitors is assumed to be approximately 6 months or less. Considering a recruitment period of 12 months and 6 months of follow up after LPFV, the expected 95% CIs for a median PFS for overall, 2nd line, and 3rd line patients with different sample sizes are presented in Table 10-1.

Table 10-1 Sample size and estimated 95% CI for median PFS

Patient population	Median PFS (months)	Sample size (N)	95% CI of median PFS (month)	Width (month)
Overall	5	90	3.96, 6.31	2.35
		100	4.01, 6.24	2.23
		110	4.05, 6.17	2.12

Patient population	Median PFS (months)	Sample size (N)	95% CI of median PFS (month)	Width (month)
2 nd line	6	30	3.95, 9.12	5.18
		40	4.17, 8.62	4.45
		50	4.34, 8.30	3.96
3 rd line	4	50	2.96, 5.40	2.44
		60	3.04, 5.26	2.22
		70	3.10, 5.16	2.05

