2.2 Rationale for the study design

In a retrospective study, [Nadal et al \(2016\)](#) reported an ORR of 27% in mRCC patients treated with VEGFR-TKI therapy after any PD-1 combination, with median PFS (mPFS) of 6.9 months (95% CI: 3.7 to 10.1). [Albiges et al \(2015\)](#) reported a median time to treatment failure of 6.9 months and 5.7 months in patients who received VEGFR-TKI and mTOR inhibitors after checkpoint inhibitor, respectively.

The efficacy and safety of anti-VEGF TKI after immune checkpoint inhibitor therapy need to be studied in a prospective trial. Since the aim of the study is to evaluate efficacy and safety of pazopanib in patients previously treated with checkpoint inhibitors, and currently there is no approved standard of care treatment for this specific patient population, no control arm has been included in the trial design. This trial is neither designed nor intended to compare efficacy and

safety to a standard of care, but to address the use of TKI therapy post immune checkpoint inhibitor. Results will be evaluated in light of previously reported data in similar populations in the context of the evolving RCC treatment landscape.

There are several ongoing trials evaluating immune checkpoint inhibitor combinations (IO-IO) or IO-Tyrosine Kinase Inhibitor (TKI) combinations as 1st line therapy, and IO is expected to become the standard of care in 1st line therapy. Data collected from the use of pazopanib in the 2nd line setting post-IO therapy will be more relevant, but these patients may also be more difficult to recruit for this study based on local treatment practices. Given the very specific patient population, a sample size of 100 patients is based on the estimated feasibility of enrolling a sufficient number of relevant patients in a timely manner, and not based on any statistical power considerations. This sample size will provide 2.78 months precision with a 95% CI of (4.77, 7.55) for an estimate median PFS of 6 months (overall). For 2nd line and 3rd line patients, the precision with a 95% CI for estimated PFS is provided in [Section 10.8](#).

Therapeutic lines of pazopanib – whether in the 2nd- or 3rd-line setting - will be tracked at screening using Integrative Response Technology (IRT) with an enrollment cap to ensure that approximately 40 patients enroll with pazopanib administered as 2nd-line treatment.

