5.4 Statistical models

5.4.1 Primary analysis

Analysis of time to events Data

Hypothesis and test statistic

Not applicable.

Kaplan-Meier estimates

An estimate of the survival function in each treatment group will be constructed using Kaplan-Meier (product-limit) method as implemented in PROC LIFETEST with METHOD=KM option. The PROC LIFETEST statement will use the option CONFTYPE=LOGLOG.

Median survival for each treatment group will be obtained along with 95% confidence intervals calculated from PROC LIFETEST output using the method of [\[Brookmeyer and Crowley 1982\]](#). Kaplan-Meier estimates of the survival function with 95% confidence intervals at specific time points will be summarized. The standard error of the Kaplan-Meier estimate will be calculated using Greenwood's formula [\[Collett 1994\]](#).

Treatment of ties

The STRATA statement in LIFETEST procedure will be used to analyze time to event data with ties.

Analysis of Binary Data

Single arm study

Confidence interval for response rate

Responses will be summarized in terms of percentage rates with $100(1 - \alpha)\%$ confidence interval using exact binomial confidence interval (implemented using SAS procedure FREQ with EXACT statement for one-way table [Clopper and Pearson 1934]).

Multiplicity adjustment

Not applicable.

Key secondary analysis

Not applicable.

6 Reference

1. Brookmeyer R and Crowley J (1982). A Confidence Interval for the Median Survival Time. *Biometrics*, 38, 29 - 41.
2. Celli, et al (2007) Development and Validation of a Scale to Measure Disease-Related Symptoms of Kidney Cancer. *Value in Health*; Vol. 10
3. Clopper CJ and Pearson ES (1934). The use of confidence or fiducial limits illustrated in the case of the binomial. *Biometrical*, 26, 404-413.
4. Collet D (1994). Modelling survival data in medical research. London, Chapman & Hall.
5. FDA briefing Document Oncologic Drugs Advisory Committee Meeting, July 24, 2012, Evaluation of radiologic review of progression-free survival in Non-hematologic malignancies.
<http://www.fda.gov/downloads/advisorycommittees/committeesmeetingmaterials/drugs/oncologicdrugsadvisorycommittee/ucm311141.pdf>
6. Nadal, et al (2016) Safety and clinical activity of vascular endothelial growth factor receptor (VEGFR)-tyrosine kinase inhibitors after programmed cell death 1 inhibitor treatment in patients with metastatic clear cell renal cell carcinoma. *Annals of Oncology* 27:1304-1311

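### The stated precision for median PFS comes from an exponential-model interval; the planned Kaplan-Meier interval is about 21% to 40% wider

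*Protocol*

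**What the plan says.** The study tests no hypothesis. Protocol Section 10.8 states: "Since there is no formal hypothesis testing, sample size for this study is not based on any statistical power consideration". On size it says: "A total of approximately 100 patients (with approximately 40 patients receiving pazopanib as 2nd-line therapy) are planned to be enrolled and treated in this study". The precision table rests on these timing assumptions: "Considering a recruitment period of 12 months and 6 months of follow up after LPFV". On that basis "the expected 95% CIs for a median PFS for overall, 2nd line, and 3rd line patients with different sample sizes are presented" in Table 10-1, and SAP Section 3.1 repeats the figures in its Table 3-1. The assumed medians are 5 months overall, 6 in second line and 4 in third line. Section 2.2 gives a further figure: "This sample size will provide 2.78 months precision with a 95% CI of (4.77, 7.55) for an estimate median PFS of 6 months (overall". Neither document names the interval method behind these figures or mentions an exponential assumption.

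For the analysis, Protocol Section 10.4.2 says: "An estimation of the median PFS with 95% confidence intervals will be provided in the FAS population". The estimator there and in SAP Section 2.5.2 is Kaplan-Meier. SAP Section 5.4.1 specifies the Brookmeyer-Crowley interval, with the log-log transformation in PROC LIFETEST: "Median survival for each treatment group will be obtained along with 95% confidence intervals calculated from PROC LIFETEST output using the method of" that name. No parametric PFS analysis is planned anywhere.

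**The concern.** A fitted exponential model uses every event and all follow-up time to estimate one rate, and so gets a narrow interval for the median. A Kaplan-Meier median uses only what the curve shows near 50%, so its interval is wider on the same data. If the table was built with the first method and the report will use the second, the table overstates what the trial will show.

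With no hypothesis and no power, the interval width is the only quantitative description of what about 100 patients (40 second-line) can deliver. The Amendment 1 rationale also quotes the 2.78-month figure when it explains the reduction from 140 to about 100 patients. The second- and third-line rows matter because line of therapy is a planned PFS subgroup and enrollment is managed to obtain about 40 second-line patients.

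A smaller point is that, for the same 100 patients overall, Section 2.2 gives a width of 2.78 months (median 6) and Table 10-1 gives 2.23 (median 5), with no explanation of the change.

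**Working it through.** **Inputs.** From Protocol Section 10.8: 12 months of recruitment (taken as uniform), 6 months of follow-up, and the medians m and sizes N in Table 10-1. From Section 2.2: m = 6, N = 100. The documents' sample size sections state no dropout, so it is zero in the main calculation.

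**Step 1: reproduce the stated figures.** With λ = ln 2/m, the probability of an observed event is

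P = 1 − [exp(−6λ) − exp(−18λ)]/(12λ),

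which gives 0.788 (m = 5), 0.730 (m = 6) and 0.851 (m = 4). Expected events are d = N·P, and the interval is m·exp(±1.96/√d). For N = 100, m = 5: d = 78.79, 1.96/√78.79 = 0.2208, and 5·exp(±0.2208) = 4.01 to 6.24, as stated. All ten figures match. Two other exponential intervals do not: for this row the chi-square form gives 4.06 to 6.32 and m(1 ± 1.96/√d) gives 3.90 to 6.10.

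**Step 2: why the planned interval is wider.** Follow-up is at least 6 months, so there is no administrative censoring before the median when m ≤ 6. The Kaplan-Meier variance at the median is then 0.25/N and the density there is ln 2/(2m). On the log scale the standard error of the median is 1/(ln 2·√N), against 1/√(N·P) for the exponential model. The ratio is √P/ln 2: 1.28 (m = 5), 1.23 (m = 6), 1.33 (m = 4). For N = 100, m = 5 the simple large-sample interval is 5·exp(±1.96/(0.6931·10)) = 3.77 to 6.63, width 2.87.

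**Step 3: the log-log Brookmeyer-Crowley interval itself.** Its expected limits solve ln(t/m) = ±1.96·√g(t)/(λt), where g is the Greenwood sum, equal to (exp(λt) − 1)/N before any censoring. For N = 100, m = 5 at t = 3.65: λt = 0.506, g = 0.00659, the right side is −0.314, and ln(3.65/5) = −0.315. The table sets these limits and a simulation (4,000 trials per row; mean width of finite intervals) beside the stated figures.

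| Row | m | N | d | Stated = Step 1 | Stated width | Planned interval, large-sample (width) | Simulated mean width | Excess over stated |
|---|---|---|---|---|---|---|---|---|
| Overall | 5 | 90 | 70.91 | 3.96–6.31 | 2.35 | 3.58–6.59 (3.01) | 2.95 | 26% |
| Overall | 5 | 100 | 78.79 | 4.01–6.24 | 2.23 | 3.65–6.51 (2.85) | 2.91 | 30% |
| Overall | 5 | 110 | 86.67 | 4.05–6.17 | 2.12 | 3.71–6.43 (2.72) | 2.65 | 25% |
| 2nd line | 6 | 30 | 21.88 | 3.95–9.12 | 5.18 | 3.12–9.73 (6.61) | 6.27 | 21% |
| 2nd line | 6 | 40 | 29.18 | 4.17–8.62 | 4.45 | 3.49–9.11 (5.62) | 5.55 | 25% |
| 2nd line | 6 | 50 | 36.47 | 4.34–8.30 | 3.96 | 3.74–8.72 (4.97) | 5.09 | 29% |
| 3rd line | 4 | 50 | 42.56 | 2.96–5.40 | 2.44 | 2.50–5.75 (3.26) | 3.28 | 34% |
| 3rd line | 4 | 60 | 51.07 | 3.04–5.26 | 2.22 | 2.62–5.59 (2.96) | 3.10 | 40% |
| 3rd line | 4 | 70 | 59.59 | 3.10–5.16 | 2.05 | 2.72–5.46 (2.74) | 2.66 | 30% |
| Section 2.2 | 6 | 100 | 72.95 | 4.77–7.55 | 2.78 | 4.38–7.83 (3.45) | 3.52 | 27% |

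Median simulated widths exceed the stated ones by 21% to 36%. In second line the upper limit is not reached in about 3% of trials at N = 40 and 10% at N = 30; those trials are left out of the mean widths.

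**Step 4: sensitivity.**
- With 24 months of follow-up instead of 6, the large-sample widths hardly move: 2.85 (overall, m = 5), 3.42 (overall, m = 6), 5.49 (2nd line, N = 40) and 2.96 (3rd line, N = 60).
- With 24 weeks of follow-up and an assumed 10% yearly dropout, widths are 1.25 to 1.36 times the stated ones on these same four figures.
- With 8-weekly scans, mean widths remain 14% to 31% above the stated ones. Median-width ratios are more erratic because limits fall on scan dates.

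**The case against.** The strongest reply is that no precision target exists. Section 2.2 bases N = 100 on feasibility, Amendment 1 gives the treatment landscape and recruitment as its reasons, and no threshold or decision depends on Table 10-1. The reported interval will be valid whatever the table says. Each figure is also arithmetically right under its own model, so this could be called an undeclared planning approximation. All of that stands, and it limits the consequence. It does not make the stated widths right for the interval that the plan says it will report.

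A second reply is that the simulation treats progression as observed exactly, whereas scans are 8-weekly. This softens one figure: the stated width is met in roughly 12% to 31% of simulated trials with exact times, but in about 27% to 53% with scan-based times. The mean excess shrinks but does not vanish. Scans also shift the limits later if the assumed median means true progression time rather than scan-detected PFS. The documents do not say which is meant, so any replacement limits are illustrative until that is settled.

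Third, 2.78 and 2.23 months are not in numerical conflict: each is correct for its own median, and Section 10.8 assumes about 6 months or less. That point is a request for consistency and does not bear on the main finding.

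**Conclusion.** The concern holds. The stated precision is that of an exponential-model interval, and the planned Kaplan-Meier interval is about 21% to 40% wider by simulated mean width (24% to 34% by the large-sample calculation for the three planned group sizes and the Section 2.2 figure). The gap is largest for the 60 third-line patients. It comes from the estimator, so longer follow-up does not close it. As a measure of scale, the planned interval would need about 163 patients overall at a median of 5 months, 153 at 6 months, 62 in second line and 106 in third line to reach the stated widths.

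The exponential origin is inferred, because the documents do not name it, but ten matches out of ten to two decimals leave little doubt. The percentages assume exponential PFS and uniform accrual, and they vary with mean versus median width and with scan timing. The direction does not change in any case examined. No error rate or decision rule is affected; the advertised precision is what is wrong.

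**What to change.** Recompute Protocol Table 10-1 and SAP Table 3-1 for the Kaplan-Meier median with the log-log Brookmeyer-Crowley interval, and name the method and the survival assumption beside the table. Approximate widths to expect are 2.9 months overall (N = 100, m = 5), 5.6 in second line (N = 40) and 3.0 to 3.1 in third line (N = 60), with a note that the second-line upper limit may not be estimable. State whether the assumed medians refer to scan-detected PFS. In Section 2.2, replace 2.78 with the matching figure (about 3.5 if the median stays at 6), and use one overall median there and in the tables.

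The minimum alternative is a sentence saying that the figures assume an exponential model and that the reported interval will be wider, by about 20% to 40%. Either way the cost is revised text and a less favourable stated precision. N and the planned analysis do not change.
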